5.2.3 Timing of Dose Administration

Study treatment should be administered on Day 1 of each 3-week cycle after all procedures/assessments have been completed as detailed on the Study Flow Chart (Section 6.0). Trial treatment may be administered up to 3 days before or after the scheduled Day 1 of each cycle due to administrative reasons.

Study treatments will be administered on an outpatient basis.

Pembrolizumab 200 mg will be administered as a 30 minute IV infusion every 3 weeks for a total of 2 cycles.

5.2.4 Trial Blinding/Masking

This is an open-label trial; therefore, the Sponsor, investigator and subject will know the treatment administered.

5.3 Randomization or Treatment Allocation

Patients will be enrolled sequentially without randomization. According to a standardized, dose escalating, phase 2 safety design a total of 20 patients may be enrolled.

Initially 3 patients will be studied at 200 mg given at weeks 1 and 4 by IV infusion. These patients will be followed for safety assessments every 3 weeks during the treatment phase and at 30 and 90 days post-op visits during the follow-up phase. If < 2 patients in the initial cohort of 3 experience a grade >3 drug related adverse event then a subsequent cohort of 17 patients at 200 mg dose will be enrolled.

The following stopping rules will apply: if at any time ≥ 3 patients experience a drug related grade 4 adverse event including bowel perforation or any drug related grade 3 skin or gastrointestinal adverse event without clinical improvement within 2 weeks of study drug discontinuation and/or initiation of corticosteroid therapy to treat the adverse event; no additional patients will be enrolled. If any grade 3 or higher adverse event that is possibly, probably or definitely related to study drug, with the exception of any grade 3 or higher adverse events that is potentially treatable with steroids and improves to grade 1 or better within 2 weeks of steroid therapy initiation and/or study treatment discontinuation, the above stopping rule would apply. Also excluded will be grade 3 lipase elevation as this is common with this agent but is almost universally asymptomatic. Grade 4 lipase elevation will be criteria for stopping. If during monitoring, a patient is found to have disease progression within the treatment study period then this will be counted as a grade 4 toxicity event and the above stopping rule would apply. If there is a >12 week delay to surgery due disease progression, then this will be counted as a grade 4 toxicity event and the above stopping rule would apply. If a patient suffers a drug related toxicity which results in an inability to perform

radical cystectomy further study enrollment will be stopped. If there is a > 12 week delay to surgery due to a drug related toxicity in 2 or more patients, further enrollment will be stopped. Once patients have received a maximum of two doses of pembrolizumab, they will undergo surgery at approximately 6 - 8 weeks. An assessment of tumor response will not be made prior to radical cystectomy.

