2.1.1 Dosing

In the Treatment Phase, a standard 200 mg dose of pembrolizumab will be tested for safety and adverse events. The study cohort will consist of a total of 20 patients in a single arm who will receive 200 mg of pembrolizumab every 3 weeks for a total of two cycles at weeks 1 and 4 by IV infusion. These patients will be followed for safety assessments 3 weeks after receipt of their second dose (week 7 \pm 3 days). The following stopping rules will apply on a rolling basis: if ≥ 3 patients experience a drug-related grade 4 adverse event including bowel perforation or any drug-related grade 3 skin or gastrointestinal adverse event without clinical improvement within 2 weeks of study drug discontinuation and/or initiation of corticosteroid therapy to treat the adverse event, no additional patients will be enrolled (see Section 5.3 for additional stopping rules that apply). Once patients have received a maximum of two doses, they will undergo surgery at or around week 8. An assessment of tumor response will not be made prior to radical cystectomy.

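### Section 5.3 defines the event counted toward the three-patient enrolment stop in two ways that no reading makes agree, most clearly for grade 4 events that resolve on steroids

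*Combined protocol and SAP*

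**What the plan says.** Section 5.3 sets the stop in one sentence (sentence 1 below): no more patients are enrolled "if at any time ≥ 3 patients experience a drug related grade 4 adverse event including bowel perforation". A second limb of that sentence covers grade 3, for two organ classes only: "any drug related grade 3 skin or gastrointestinal adverse event without clinical improvement within 2 weeks of study drug discontinuation". Starting corticosteroids also sets that 2-week clock.

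The next sentence (sentence 2) opens with "If any grade 3 or higher adverse event that is possibly, probably or definitely related to study drug". It excepts "any grade 3 or higher adverse events that is potentially treatable with steroids and improves to grade 1 or better within 2 weeks", and its closing words give the clock for the exception and the link back to the three-patient rule: "of steroid therapy initiation and/or study treatment discontinuation, the above stopping rule would apply". Section 5.3 then also excludes grade 3 lipase elevation.

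Section 2.1.1 prints sentence 1 only, including the limit "without clinical improvement within 2 weeks of study drug discontinuation and/or initiation of corticosteroid therapy", and refers the reader to Section 5.3 for additional stopping rules. It also gives the size of the trial: "The study cohort will consist of a total of 20 patients in a single arm".

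**The concern.** The two sentences feed the same count but differ in three respects: organ scope (skin and gut for grade 3, against any organ), recovery test (clinical improvement, against grade 1 or better), and whether a grade 4 event that resolves is exempt. Nothing says which sentence governs.

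The rule applies on a rolling basis, so someone has to decide at the time whether a given patient adds to the count. The disputed patients are foreseeable. Section 5.2.2 says that most immune-related events were reversible and manageable with interruption and corticosteroids, and Table 3 is written for such events. The separate TOX monitoring in Section 9.3 does not fill the gap. TOX in Section 9.1.1 covers related grade 3 or higher surgical complications, related toxicity that prevents surgery, and toxic death. A severe immune-related event that resolves in time for surgery is none of these.

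**Working it through.** The plan states no stopping probability for the three-patient rule, so there is no figure to reproduce. The operating characteristics in Section 9.3 describe TOX, which is a different endpoint.

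**Step 1: classify events under each sentence.** Take drug-related events by organ (skin or gastrointestinal, other), grade (3, 4) and outcome within 2 weeks (no improvement, to grade 2, to grade 1 or better on steroids). That gives 2 × 2 × 3 = 12 types. A fall to grade 2 is taken as clinical improvement. Lipase is left out. Sentence 1 can be parsed in two ways. In parse A, the plain one, the no-improvement limit attaches to the grade 3 limb only. In parse B it also attaches to grade 4.

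| Event | Outcome within 2 weeks | Sentence 1, parse A | Sentence 1, parse B | Sentence 2 |
|---|---|---|---|---|
| Grade 3 skin/GI | no improvement | counts | counts | counts |
| Grade 3 skin/GI | to grade 2 | no | no | counts |
| Grade 3 skin/GI | to grade 1 or better | no | no | excepted |
| Grade 3 other | no improvement | no | no | counts |
| Grade 3 other | to grade 2 | no | no | counts |
| Grade 3 other | to grade 1 or better | no | no | excepted |
| Grade 4, either organ class (2 types per row) | no improvement | counts | counts | counts |
| Grade 4, either organ class | to grade 2 | counts | no | counts |
| Grade 4, either organ class | to grade 1 or better | counts | no | excepted |

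Under parse A, sentences 1 and 2 differ on 1 + 2 + 2 = 5 of 12 types: grade 3 skin/GI to grade 2, two grade 3 types in other organs, and two grade 4 types that resolve. Under parse B they again differ on 1 + 2 + 2 = 5. The grade 3 types are the same, but the grade 4 conflict moves to events that improve only to grade 2. Neither parse brings the sentences into agreement.

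**Step 2: read sentence 2 as an addition, so that an event counts if either sentence counts it.** Every grade 3 event that sentence 1 counts is already counted by sentence 2, so the skin/GI and clinical-improvement limits do no work. Under parse A all grade 4 events count, and the exception has no effect on grade 4 although it is worded for grade 3 or higher. Under parse B sentence 1 adds nothing to sentence 2, and a resolved grade 4 event is exempt. The status of that patient therefore still depends on the parse.

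**Step 3: size.** Let p be the per-patient rate of the disputed events. The documents give no value, so p is assumed. With n = 20,

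P(X ≥ 3) = 1 − (1−p)^20 − 20p(1−p)^19 − 190p²(1−p)^18

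| p (assumed) | Terms subtracted from 1 | P(X ≥ 3 of 20) | P(X ≥ 3 of 19) |
|---|---|---|---|
| 2% | 0.668 + 0.272 + 0.053 | 0.007 | 0.006 |
| 5% | 0.358 + 0.377 + 0.189 | 0.075 | 0.067 |
| 10% | 0.122 + 0.270 + 0.285 | 0.323 | 0.295 |
| 15% | 0.039 + 0.137 + 0.229 | 0.595 | 0.559 |

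The last column leaves out the 20th patient, after whom no enrolment remains to be stopped. The same table shows the effect of a wider definition: if the narrower one has a 5% rate and the broader one 10% to 15%, the chance of reaching three in 20 moves from 7.5% to between 32% and 60%.

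**The case against.** The best defence is that sentence 2 extends sentence 1 and that the two together make one workable rule. For grade 3 events this largely stands. A grade 3 gut event that improves only to grade 2, or a grade 3 event in another organ that does not recover, counts once sentence 2 is applied, whether it adds to sentence 1 or overrides it. The grade 3 lipase exclusion supports this, since it has little purpose unless grade 3 events outside skin and gut count. A reader might infer that these patients both count and do not count. The documents do not support that, because such patients drop out only if sentence 2 is ignored. The defence does not settle grade 4, as step 2 shows.

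A reader might also infer that Section 2.1.1 contradicts 5.3. It does not: it points to 5.3 for additional rules. What remains is that someone who works from 2.1.1 alone would miss grade 3 events outside skin and gut.

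Nor is this the only protection. Section 5.3 also has the gate after the first three patients, a stop if drug toxicity makes cystectomy impossible in a patient, and a stop if drug toxicity delays surgery by more than 12 weeks in two or more patients. Section 9.3 adds a monthly safety report to the Medical Monitor. These limit the consequence, but they do not say which events count toward the three.

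**Conclusion.** The point holds as an internal inconsistency in Section 5.3. It is sharpest for a grade 4 event that resolves to grade 1 or better within 2 weeks on steroids: on the plain parse it counts under sentence 1 and is excepted by sentence 2. The other parse moves the conflict to grade 4 events that improve only to grade 2. The two recovery tests and the two organ scopes also differ. Grade 5 is not named in sentence 1 or in 2.1.1, and is reached only through sentence 2's wider grade range.

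The size is uncertain. The chance that disputed events alone reach three in 20 runs from 0.7% at an assumed 2% rate to 60% at an assumed 15%. The upper rates may be high for resolving grade 4 events alone. A reader might take these figures as evidence that the trial is likely to be affected. The documents do not support that, because they give no event rates. The textual finding does not depend on the rates.

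**What to change.** The sponsor should reconcile the two sentences of Section 5.3 and the copy in Section 2.1.1 into one list of countable events, worded identically in both places. The list should state how four matters are handled: grade 4 events that resolve, the recovery test, organ scope, and grade 5 events. Which rule is right is for the sponsor to decide.

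Until the text is amended, the existing monthly report to the Medical Monitor can show the count under both readings, so that any difference between them is visible.

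The cost is a wording amendment to two sections and one extra tally in an existing report. Sample size and data collection do not change.

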Hyperthyroidism	Grade 2	Continue		
 Monitor for signs and symptoms of thyroid disorders.

	Grade 3 or 4	Withhold or permanently discontinue ¹	
 Treat with non-selective beta-blockers (eg, propranolol) or thionamides as appropriate 	
Hypothyroidism	Grade 2-4	Continue	
 Initiate thyroid replacement hormones (eg, levothyroxine or liothyroinine) per standard of care 	
 Monitor for signs and symptoms of thyroid disorders.
Nephritis and Renal dysfunction	Grade 2	Withhold	
 Administer corticosteroids (prednisone 1-2 mg/kg or equivalent) followed by taper. 	
 Monitor changes of renal function
	Grade 3 or 4	Permanently discontinue		
Myocarditis	Grade 1 or 2	Withhold	
 Based on severity of AE administer corticosteroids 	
 Ensure adequate evaluation to confirm etiology and/or exclude other causes
	Grade 3 or 4	Permanently discontinue		
All other immune-related AEs	Intolerable/ persistent Grade 2	Withhold	
 Based on type and severity of AE administer corticosteroids 	
 Ensure adequate evaluation to confirm etiology and/or exclude other causes
	Grade 3	Withhold or discontinue based on the type of event. Events that require discontinuation include and not limited to: Gullain-Barre Syndrome, encephalitis		
	Grade 4 or recurrent Grade 3	Permanently discontinue		

1. Withhold or permanently discontinue pembrolizumab is at the discretion of the investigator or treating physician.

NOTE:

For participants with Grade 3 or 4 immune-related endocrinopathy where withhold of pembrolizumab is required, pembrolizumab may be resumed when AE resolves to ≤ Grade 2 and is controlled with hormonal replacement therapy or achieved metabolic control (in case of T1DM).

Dose modification and toxicity management of infusion-reactions related to pembrolizumab

Pembrolizumab may cause severe or life threatening infusion-reactions including severe hypersensitivity or anaphylaxis. Signs and symptoms usually develop during or shortly after drug infusion and generally resolve completely within 24 hours of completion of infusion. Dose modification and toxicity management guidelines on pembrolizumab associated infusion reaction are provided in Table 4.

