6.0 STUDY FLOW CHART

STUDY PHASE	SCREENING PHASE	TREATMENT PHASE				FOLLOW-UP PHASE	EARLY TREATMENT DISCONTINUATION
VISIT/CYCLE	SCREENING	CYCLE #1 (Week 1)	CYCLE #2 (Week 4)	PRE-OP/SAFETY VISIT (Week 7)	SURGERY (Week 6- 8)	FOLLOW-UP	
Scheduling window (days)	-28 to -1	1(± 3)	21(± 3)	35-49(± 3)	42-56(± 3)	30 day (± 7) and 90 day (± 7) Post Op	
Informed Consent	X						
Inclusion/Exclusion Criteria	X						
Demographics/Medical history	X						
Concomitant Medications	X	X	X	X	X	X ⁸	X ⁸
Pembrolizumab Administration		X	X				
Assessment of Disease Extent ¹	X						
Review of Adverse Events	X	X	X	X	X	X	X
Full Physical Exam	X						X
Directed Physical Exam		X	X	X		X	
Vital Signs and Weight	X	X ²	X ²	X		X	X
ECOG Performance Status	X	X	X	X		X	X
Pregnancy Test	X	X ³					
PT/INR and aPTT	X ⁹	X	X	X		X	X
CBC with Diff	X ⁹	X	X	X		X	X

Proprietary Information of MD Anderson

2017-0057

January 9, 2019

Page 28

Comprehensive Metabolic Panel ⁴	X ⁹	X	X	X		X	X
Urinalysis ⁵	X ⁹	X	X	X		X	X
T3, FT4 and TSH	X ⁹	X	X	X		X	X
Pulmonary Function Tests	X						
ACTH, Cortisol	X	X	X				
ESR, CRP	X	X	X				
Testosterone, FSH, LH (males)	X	X	X				
Estrogen, FSH, LH (females)	X	X	X				
Archival Tissue Collection ⁶	X				X		
Feces and Urine for microbiome studies	X			X		X ¹⁰	
Blood for Correlative Studies ⁷	X		X	X		X	
Cystectomy					X		

¹ A complete assessment of disease extent will be made at screening per SOC guidelines, and will include but not be limited to diagnostic endoscopy with biopsy/resection of the index lesion for pathologic diagnosis. Additionally an examination and assessment for palpable disease will be made. Cross sectional imaging of the chest, abdomen and pelvis with the addition of whole body nuclear medicine bone imaging where clinically indicated will complete the staging evaluation. Exams performed within 6 weeks prior to screening will be accepted for inclusion in the study if deemed appropriate by the treating physician

² Pre and post pembrolizumab dose during treatment administration days

³ Female subjects of childbearing potential should have a negative urine or serum pregnancy test within 72 hours prior to receiving the first dose of study medication. If the urine test is positive or cannot be confirmed as negative, a serum pregnancy test will be required.

⁴ Includes: Albumin, alkaline phosphatase, ALT, AST, LDH, electrolytes, uric acid, calcium, glucose, phosphorus, magnesium, total bilirubin, total protein, BUN and creatinine

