7.1 STUDY PROCEDURES

The Study Flow Chart - Section 6.0 summarizes the trial procedures to be performed at each visit. Individual trial procedures are described in detail below. It may be necessary to perform these procedures at unscheduled time points if deemed clinically necessary by the investigator.

Furthermore, additional evaluations/testing may be deemed necessary by the investigator for reasons related to subject safety. In some cases, such evaluation/testing may be potentially sensitive in nature (e.g., HIV, Hepatitis C, etc.), and thus local regulations may require that additional informed consent be obtained from the subject. In these cases, such evaluations/testing will be performed in accordance with those regulations.

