7.13 Laboratory Assessments

Details regarding specific laboratory assessments are specified in Table 6. Laboratory tests for screening should be performed within 14 days prior to the first dose of pembrolizumab. Laboratory assessments for each subsequent visit can be conducted up to 72 hours prior to dosing/clinic visit. Results must be reviewed by the investigator or qualified designee and found to be acceptable prior to each dose of pembrolizumab.

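### Section 5.3 makes grade 4 lipase elevation a stopping criterion, but the flow chart schedules no lipase test (subject to Table 6, which is cited but absent from the available text)

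*Combined protocol and SAP*

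**What the plan says.** Section 5.3 treats lipase differently by grade. Grade 3 is taken out of the enrolment stopping rule: "Also excluded will be grade 3 lipase elevation as this is common with this agent but is almost universally asymptomatic". The next sentence reads "Grade 4 lipase elevation will be criteria for stopping". These are the only mentions of lipase in the available text.

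The flow chart in Section 6.0 schedules a metabolic panel at screening, both treatment cycles, the week 7 visit, follow-up and early discontinuation. Its footnote 4 gives the contents: "Includes: Albumin, alkaline phosphatase, ALT, AST, LDH, electrolytes, uric acid, calcium, glucose, phosphorus, magnesium, total bilirubin, total protein, BUN and creatinine".

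Section 5.2.3 has treatment given on day 1 of each cycle "after all procedures/assessments have been completed as detailed on the Study Flow Chart (Section 6.0"). Section 7.13 adds: "Results must be reviewed by the investigator or qualified designee and found to be acceptable prior to each dose of pembrolizumab". The same section states "Details regarding specific laboratory assessments are specified in Table 6". Tables 1 to 5 are in the available text; Table 6 is not.

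Section 7.1 allows for unscheduled work: "additional evaluations/testing may be deemed necessary by the investigator for reasons related to subject safety".

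**The concern.** A stopping criterion defined by a laboratory value works only if the value is measured. If lipase is tested only when someone decides to order it, whether an event is recorded depends partly on who was tested. A raised result would also have no planned pre-treatment value beside it, which makes attribution to the drug harder. Safety is the primary objective (Section 3.1.1), so uneven ascertainment of a named safety event matters even in a 20-patient single-arm study.

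Individual patients may be affected too. In Table 3, the row "All other immune-related AEs" requires permanent discontinuation for a grade 4 event. A patient with an unmeasured immune-related grade 4 elevation after dose 1 could be given dose 2.

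**Working it through.** The plan states no figure on this point, so there is none to reproduce. The check is a reading of the schedule against the criterion, followed by a count of draws.

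**1. Is lipase scheduled?**

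| Place | Laboratory content | Lipase? |
|---|---|---|
| Section 5.1.2, Table 1 | Haematology, renal, hepatic, coagulation | No |
| Section 6.0, metabolic panel (footnote 4) | 15 items, counting electrolytes as one | No (0 of 15) |
| Section 6.0, other laboratory rows | Coagulation, blood count, urinalysis, thyroid, ACTH/cortisol, ESR/CRP, sex hormones, pregnancy test | No |
| Section 7.13, Table 6 | Not in the available text | Cannot be checked |

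The text does not show whether Table 6 was lost, never existed, or is a mislabelled pointer to the Section 6.0 flow chart. If it is such a pointer, the omission is certain. If Table 6 exists and lists lipase, the main point falls away, but footnote 4 would still need aligning because dosing is tied to the flow chart.

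**2. Which existing draws could detect an event?** Inputs: 20 patients (Section 9.2) and the metabolic panel draws in Section 6.0. Laboratory work precedes dosing (Sections 5.2.3 and 7.13), so the cycle 1 draw is still pre-treatment.

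| Draw | Timing | Can show an event after treatment starts? | Can change dose 2? |
|---|---|---|---|
| Screening | Before dose 1 | No (baseline) | No |
| Cycle 1 | Before dose 1 | No (baseline) | No |
| Cycle 2 | After dose 1, before dose 2 | Yes | Yes |
| Week 7 | After dose 2 | Yes | No |
| Day 30 after surgery | After dose 2 | Yes | No |

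- Samples able to detect an event: 3 × 20 = 60.
- Of these, before dose 2: 1 × 20 = 20.
- Baseline samples needed: 1 × 20 = 20, from either screening or cycle 1.
- The follow-up column also covers day 90. Using that draw would add 1 × 20 = 20.

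The counts assume that all 20 patients attend every draw. No stopping probability can be calculated, because the documents give no rate of grade 4 lipase elevation.

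**3. What does the criterion trigger?** The other sentences in Section 5.3 state their consequence. Progression during treatment counts as a grade 4 event under the 3-patient rule. One patient unable to have cystectomy because of drug toxicity stops enrolment. Two patients with a toxicity-related surgical delay beyond 12 weeks stop it. The lipase sentence gives neither a count nor a link to the 3-patient rule. Because it follows the exclusions from that rule, it can be read as restoring grade 4 lipase as a counted event. Read literally, it could also mean that one event suffices.

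**4. Does this reach the TOX rule?** Section 9.1.1 defines TOX by related grade 3 or higher surgical complications within 30 days, related toxicity that prevents surgery, and toxic death. A lipase value alone meets none of these. The monitoring boundaries and operating characteristics in Section 9.3 are therefore unaffected.

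**The case against.** The strongest reply is that Section 7.13 names Table 6 as the source for laboratory detail and we cannot see it, while Section 7.1 says that the flow chart only summarises procedures. That stands as a condition on the whole point. It does not remove the point, because Section 5.2.3 ties dosing to the flow chart, and footnote 4 itemises the panel without lipase.

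A second reply is that a stopping event need not have a scheduled test. Progression counts if it is found, yet disease extent is formally assessed only at screening. On this view the lipase sentences merely classify a value if one is obtained, with testing for cause under Section 7.1. That is a possible reading. But progression may show itself at the scheduled examinations or at surgery, whereas a lipase elevation is known only if measured, and Section 5.3 sets the criterion on the elevation without requiring symptoms. Adverse event review under Section 7.6 would prompt testing in symptomatic patients only.

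A third reply, which stands in full, is that routine testing has a cost. The grade 3 exemption covers the enrolment stopping rule and nothing else. Table 3 still advises withholding or discontinuing drug for other grade 3 immune-related events and provides for corticosteroids, with a taper of at least 4 weeks. Incidental findings could therefore disrupt a short pre-operative window unless the protocol addresses them.

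A reader might also infer that grade 4 elevations are typically silent. The protocol describes only grade 3 that way.

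**Conclusion.** The gap is real on the available text and conditional on Table 6. If Table 6 does not list lipase, a named stopping event rests on discretionary testing without a planned baseline. Existing draws could supply about 60 informative samples in 20 patients, 20 of them before dose 2.

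Stronger readings are not supported:

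- The criterion is not inoperable, because unscheduled testing is allowed.
- The formal safety monitoring is not compromised, because TOX does not depend on lipase.
- The text does not establish that the event counts under the 3-patient rule, nor that one event stops enrolment. The sentence is ambiguous.
- The dose 2 consequence is a possibility. It needs an immune-related grade 4 event between the doses, and only the cycle 2 draw could prevent it.

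This is a minor, cheap safety improvement.

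**What to change.** 1. Confirm what Table 6 contains, or correct the reference.
2. If lipase is absent, add it to the metabolic panel blood at one pre-treatment draw (screening or cycle 1), before dose 2, at week 7, at day 30 after surgery and at the early discontinuation visit. Add day 90 if the Section 5.3 rule, which applies at any time, is meant to run that long. Section 8.1 ends reporting of all adverse events 30 days after surgery, but serious events are reported until 90 days after treatment ends (30 if new anticancer therapy starts). Align footnote 4.
3. State in Section 5.3 whether a drug-related grade 4 lipase event counts towards the 3-patient rule or stops enrolment alone.
4. Keep the grade 3 exemption, and state in Table 3 that an isolated, asymptomatic grade 3 lipase elevation does not by itself require withholding pembrolizumab or giving steroids.

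The cost is one analyte on existing draws: 4 × 20 = 80 scheduled tests, or 5 × 20 = 100 with day 90, plus at most one for each patient with an early discontinuation visit. No visit or procedure is added. The main downside is incidental asymptomatic elevations, which item 4 is meant to contain.
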